## 9.2. CONSENT

*Describe how and when program applicants will be informed of the study and will have the option of agreeing (i.e., consenting to) or declining to participate in the study.*

Fathers will be recruited or referred to *All in Dads!*. Case Managers will contact fathers to fully explain the project, including the research component involving surveys at the start of workshops, the end of workshops, and 12-months following enrollment into the project. General intake information and the nFORM Applicant Characteristics Survey will be administered. At that point, an nFORM profile will be created. If the applicant decides to enroll in the project, the Case Manager will schedule the father for a virtual orientation session. If the applicant decides not to enroll in the project, he will be provided with resources and referrals to other programs. From there, fathers will attend their scheduled virtual orientation with a workshop facilitator where they will be reminded that participation in the project is voluntary, that they can drop out of the project at any time for any reason without consequences after completing the consent form and will be given the opportunity to leave the orientation session if they desire. If the applicant agrees to participate in the project, he will complete a consent form along with a release of information form, media release form, and the nFORM Entrance Survey. Informed consent will take place prior to program enrollment and the collection of evaluation data.

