## 9.5. TRACKING PARTICIPANTS AND REDUCING ATTRITION

*If participants will complete post-program and/or follow-up surveys, please provide estimated response rates for each wave of data collection listed in 10.3. Please describe plans for tracking*

*participants and reducing attrition below. Note: If no post-program or follow-up surveys are proposed, this issue does not need to be addressed.*

For each wave of data collection listed in 10.3, what is your estimated response rate?	Baseline	T1: 100%-done at time of enrollment/orientation
	Wave 1	T2: 90%-Estimated completion rate
	Wave 2	T3: 70%-Estimated 1 year follow-up
	Wave 3	
	Wave 4	

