Missing data for the implementation outcomes could happen as a result of programmatic data entry issues. For the sake of this evaluation, we assume that any primary or support services received by a participant are being accurately logged into nFORM, so a lack of documented attendance, service contacts, referrals, etc. is indicative of lack of services (i.e., a participant not receiving the program components as intended).

Assessing non-response bias

We will conduct response rate analysis for each primary outcome of interest to assess non-response bias and adjust for threats to internal validity. Using data from the Applicant Characteristics Survey, we will look at demographics (race, ethnicity, age, education level) and primary reason for joining the program among participants who fall into each of the following categories: 1) non-respondents who answered no surveys after the ACS, 2) respondents who completed the pre-survey only, 3) respondents who completed the post-survey only, and 4) respondents who completed both the pre- and post-survey (complete case).

Analytic approach

The main goal of this descriptive study is to assess pre-post change scores in the attitudinal outcomes listed above and assess pre-to-one-year follow-up change scores in the behavioral outcomes listed above among program participants before and after primary workshops. We will use paired sample t-tests to assess the magnitude and significance of changes among program participants in the analytic sample for each outcome. For binary economic stability outcomes, we will descriptively report the percent of participants who opened a checking or savings account one year after enrollment, compared to the percent who had opened these accounts before the program. We will adjust our p-values for multiple hypothesis testing and report the adjusted p-values in the appendix of the final report.

2. Data Archiving and Transfer

Briefly describe the planned approach data arching and transfer by addressing questions below.

What procedures and parameters are established for all aspects of data/information collection necessary to support archiving data collected as part of the evaluation?

Examples include informed consent, data maintenance, de-identifying data procedures.

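### The non-response check omits baseline outcome scores and attendance, does not clearly classify one-year response, and names no method for the adjustment it promises

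*SAP*

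**What the plan says.** SAP section 1, under the non-response heading, plans a response analysis for each primary outcome, to gauge bias from non-response and "adjust for threats to internal validity". The content is a comparison on applicant-survey (ACS) data: "we will look at demographics (race, ethnicity, age, education level) and primary reason for joining the program". Four groups are compared. The first is "non-respondents who answered no surveys after the ACS"; the middle two completed only the pre-survey or only the post-survey; the last is "respondents who completed both the pre- and post-survey (complete case").

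Other parts of the plan bear on this:

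- **Study sample (SAP section 1).** Recorded consent is required. Attitudes need entrance and exit surveys; behavioural outcomes need entrance and follow-up surveys.
- **Missing outcomes and main test (SAP section 1).** Missing outcomes are not imputed. Change is tested by paired t-test in the analytic sample, with no weights or covariates named. The binary account items are reported descriptively.
- **Dosage model (SAP section 1).** Attendance hours and baseline covariates, including developmental starting points, appear here.
- **Response rates (Protocol 9.5).** 100% at baseline, 90% post-program, and at one year "T3: 70%-Estimated 1 year follow-up".
- **Order of intake (Protocol 9.2).** "General intake information and the nFORM Applicant Characteristics Survey will be administered" before the father decides whether to enroll. Consent comes later, at orientation.

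**The concern.** The study has no control group. Protocol section 5 reads change from baseline to follow-up as the largest benefit that can be credited to the program, and Protocol 1.2 labels all four questions confirmatory. If fathers who can still be reached at one year have changed more than those who cannot, the complete-case mean overstates average change, and a significant t-test may reflect who answered.

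The planned check is meant to guard against this, but it leaves out two obvious candidates for driving both response and change: where a father started on the outcome and how much of the program he attended. Balance on the listed ACS variables could therefore reassure wrongly. Finding an imbalance would not help much either, because the plan does not say what would be done about it.

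**Working it through.** The documents give no figure for non-response bias, so there is none to reproduce. The check has two parts.

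**1. The text, side by side**

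- *Wave.* The response groups use pre and post. The behavioural outcomes (R1–R3) use entrance and one-year follow-up. Post may be loose wording for whichever later survey applies, but the SAP does not say so.
- *Variables.* The check uses four demographics and the reason for enrolling. Baseline outcomes (Protocol 9.3) and attendance hours (nFORM) are held but enter only the dosage model.
- *Adjustment.* The SAP names no weights, no covariates in the t-test, no outcome imputation and no sensitivity analysis.
- *Denominator.* The ACS precedes consent, so the first group may include applicants who never consented. It may also hold consented fathers: Protocol 9.2 puts the entrance survey at orientation, but the measures table in 9.3 puts it at the first workshop session.

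**2. Illustrative size**

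Inputs: 70% response at one year and 90% post-program (Protocol 9.5); analytic n = 483 and two-sided alpha 0.05 (Protocol 8.2). Taking 483 as the one-year complete cases implies 483 / 0.70 = 690 enrolled and 207 lost; the documents do not state 690. Let d be responder minus non-responder mean change, in SD of change. Every value of d is an assumption.

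The mean for all enrolled is 0.70 × (responder mean) + 0.30 × (non-responder mean). The complete-case mean is the responder mean. The difference is

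bias = 0.30 × d.

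With no true average change, the false-positive rate is

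Φ(bias × √483 − 1.96) + Φ(−bias × √483 − 1.96), where √483 = 21.98.

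If the target is completers only, and everyone missing the post-survey is a non-completer who is also lost at one year (an assumption), loss is 1 − 0.70/0.90 = 22.2%.

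| Assumed d | Bias, 30% loss | False-positive rate | Bias, 22% loss | False-positive rate |
|---|---|---|---|---|
| 0.1 | 0.03 SD | 10% | 0.022 SD | 8% |
| 0.3 | 0.09 SD | 51% | 0.067 SD | 31% |
| 0.5 | 0.15 SD | 91% | 0.111 SD | 69% |

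For scale, a paired test at n = 483 with 80% power detects (1.960 + 0.842)/21.98 = 0.127 SD. Protocol 8.2 gives 0.030, which this formula does not reproduce; that is a separate matter.

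**Simulation of the mechanism.** 1,000 runs, 690 enrolled, about 70% response, true mean change zero. Assumed: response logit = 0.95 + 0.5 × attendance − 0.3 × baseline score; change loads +0.35 on attendance and −0.35 on baseline. Two standardised variables stand in for demographics.

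| Estimate | Demographics unrelated to attendance | Correlation 0.3 with attendance |
|---|---|---|
| Complete case | bias 0.077 SD, 40% false positives | 0.079 SD, 42% |
| Weighted on demographics | 0.077 SD, 40% | 0.075 SD, 38% |
| Weights add baseline score and attendance | 0.000 SD, 5% | 0.002 SD, 4% |
| Runs where demographics differ by response | 5% | 32.5% |

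The third row is clean only because the assumed response depends on nothing unmeasured.

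**The case against.** Four objections have force.

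- *The check is not empty.* It includes the reason for enrolling as well as demographics, and it can show loss related to any listed variable. A reader might infer that it cannot detect bias at all. The documents do not support that; the gap is loss driven by baseline score or attendance that the listed variables do not capture.
- *Consent.* A reader might infer that the first group does contain people who never consented. The SAP speaks of participants in this paragraph and requires consent for the study sample, and the CONSORT diagram that might settle the denominator is not visible in the copy reviewed. Only the possibility stands. Removing everyone with just an ACS could also discard consented fathers who were lost early.
- *The target may be completers.* Protocol 1.2 and section 4 frame the questions around fathers who complete services, while the intent-to-treat wording in 9.5 concerns whom to follow up. This shrinks the bias but does not remove it.
- *The sizes are assumed.* They also ignore the planned multiplicity adjustment, although those p-values go to an appendix, and they do not apply to the descriptive R3 items.

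It could also be said that the study is only descriptive. It still runs significance tests, labels its questions confirmatory and promises an adjustment.

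**Conclusion.** The point stands in this form: the SAP promises an adjustment it does not specify, its response groups as written do not cover the one-year wave, and its comparison leaves out two variables already held that plausibly drive loss and change. The denominator needs defining.

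The documents do not show that the results will be biased. The rates of 10%, 51% and 91% (8%, 31% and 69% for completers) are conditional on assumed gaps of 0.1, 0.3 and 0.5 SD, on the planned response rates being realised, on n = 483 complete cases at one year, and on unadjusted tests of the continuous R1 and R2 outcomes. They show only that moderate selective loss would matter at this sample size. This is an improvement the plan should make; it does not invalidate the design.

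**What to change.** 1. Define the denominator as consented enrollees. Exclude only applicants who never consented, and keep consented fathers who have no later survey.
2. Classify response separately at post-program (for R4) and at one year (for R1–R3). This also brings R3 and R4 into a check now worded for primary outcomes only.
3. At each wave, compare responders with non-responders on the baseline value of each outcome and on attendance hours, as well as the ACS variables already listed.
4. As the promised adjustment, report a sensitivity estimate of mean change (for R3, of the percentages) among consented fathers with a baseline survey. Weight it by the inverse probability of follow-up response, modelled on the variables in step 3. State that it does not remove bias from unmeasured causes.

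The unweighted paired t-test can remain the main analysis. The cost is a logistic response model, one table and a somewhat wider interval for the weighted estimate. No new data are needed.

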## 5. RESEARCH DESIGN

For each research question, briefly describe why the research design proposed will answer each research question(s). State whether the proposed evaluation is a descriptive or impact evaluation and justify why the proposed research design is best suited to answer the research question(s).

Research Question	Design	Justification
R1	Pre to follow-up assessment will estimate the impact of AID! participation on healthy parenting behavior .	Healthy change reported by participants in their parenting behavior from pre to 1-year follow-up estimates the maximum amount of benefit that can be attributed to AID! services in the absence of a counterfactual.
R2	Pre to follow-up assessment will estimate the impact of AID! participation on healthy co-parenting behavior .	Healthy change reported by participants in their co-parenting behavior from pre to 1-year follow-up estimates the maximum amount of benefit that can be attributed to AID! services in the absence of a counterfactual.
R3	Pre to follow-up assessment will estimate the impact of AID! participation on healthy financial behavior .	Healthy change reported by participants in their financial behavior from pre to 1-year follow-up estimates the maximum amount of benefit that can be attributed to AID! services in the absence of a counterfactual.
R4	Pre to post assessment will estimate the impact of AID!	Healthy change reported by participants in their parenting attitudes from pre to post estimates the maximum amount of benefit that

participation on **healthy parenting attitudes**.

can be attributed to AID! services in the absence of a counterfactual.

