All in Dads! Healthy Marriage and Responsible
Fatherhood Program Evaluation

Statistical Analysis Plan

NCT05194020

October 17, 2024

1. Data Analysis

Briefly describe the planned approach for data analysis. If an impact analysis is proposed, name the key dependent and independent variables, and describe any methods to minimize Type I error (i.e., finding positive impacts by chance) such as limiting the number of impacts to be analyzed and/or multiple comparison correction. Describe proposed approach(es) for addressing missing data.

Identify study sample

The study sample includes participants who: 1) gave recorded informed consent to be part of the study, and 2) took both an entrance and exit survey (for attitudinal outcomes) or entrance and follow-up survey (for behavioral outcomes). The CONSORT diagram in Figure 2 shows exclusion criteria and the anticipated size of the overall study sample. The analytic sample for particular outcome measures will vary based on missing data.

Defining analysis measures

For each outcome construct, we have identified the relevant measures from nFORM that are theoretically aligned with that construct. We will generate a correlation matrix between items in a given construct to ensure that theoretically related items are also empirically related in our data set. Items that are not strongly correlated with other items in a construct will be removed as necessary. Factor analysis will be used to ensure that all construct items hang together (using an alpha of 0.7 or higher as the threshold). If an alpha of 0.7 cannot be obtained, that outcome will be removed.

Once we are confident that all of the items align with a given construct, we will create a composite measure by taking an average of the scores on each non-missing item in the construct. The measure definition matrix below provides information on each proposed outcome. For composite measures, a change score will be calculated between a participant's pre-program composite score and post-program composite score. For standalone survey items, a change score will be calculated between a participant's pre-survey and post-survey responses.

For the sake of consistency and simplicity, parenting and co-parenting analyses will use a participant's youngest child as the focal child.

Model Specification to Predict Outcomes With Dosage

Construct by Outcome	Dependent Variables (follow-up)	Response Codes for Dependent Variables	Dependent Variable Type	Independent Variables

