Primary outcome:				
Parenting Behavior: 1 item	HOURSFU	# hours spent with child		Dosage: hours of attendance per service
	REACHFU	1 = Almost every day to 5 = never in past month	Continuous	

1 item 11 scaled items Co-parenting Behavior: 11 scaled items	ENGAGFU	1 = never to 5 = every day or almost every day	(using nFORM data); Co-variates: development starting points, risk - family structure, demographics, socioeconomic (ACS & OLLE survey data at baseline)
	COPARFU	1 = strongly disagree to 5 = strongly agree	
		1 = yes, 0 = no	

Secondary outcome:

Parenting Attitudes: 7 scaled items Financial Readiness 1 item 1 item	PATTFU	1 = always to 5 = never	Continuous	Dosage: hours of attendance per service (using nFORM data); Co-variates: development starting points, risk - family structure, demographics, socioeconomic (ACS & OLLE survey data at baseline)
	SAVFU			
	CHECKFU	1 = yes, 0 = no	Dichotomous	

Handling missing data

Outcomes

When creating the composite measures for co-parenting and parenting relationships, we will create a composite score by taking the average of multiple individual items. For these measures, our current plan is to use 20% as a threshold for allowable missing items, based on guidance from evaluation technical assistance resources. This plan is contingent on the final distribution of missing data in our data set. With a 20% threshold, if a respondent is missing more than 1 item used for creating the co-parenting construct or more than 2 items for creating the parenting construct, the respondent will be assigned a missing value for that construct. We will not be imputing truly missing values for outcomes. To create a construct score, the average will divide by the number of non-missing values in the construct.

Participants who have not seen their child within the past month will have their parenting behavior responses set to "Never" (1) and will be included in the analytic sample for that outcome.

For outcomes that use single survey items, participants who do not respond to the item on either the pre- or post-survey will be excluded from the analytic sample for that outcome.

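### The SAP's non-response check for the primary outcomes groups fathers by pre- and post-survey, although both outcomes rest on the one-year follow-up

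*SAP*

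**What the plan says.** SAP section 1, under *Assessing non-response bias*, states: "We will conduct response rate analysis for each primary outcome of interest to assess non-response bias and adjust for threats to internal validity". It will compare demographics and reason for joining across four groups: fathers with no survey after the Applicant Characteristics Survey, those with the pre-survey alone, those with the post-survey alone, and "respondents who completed both the pre- and post-survey (complete case".

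On which surveys the primary outcomes use:

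- SAP, *Identify study sample*: the sample is those who "took both an entrance and exit survey (for attitudinal outcomes) or entrance and follow-up survey (for behavioral outcomes".
- SAP, *Analytic approach*: the plan is to "assess pre-to-one-year follow-up change scores in the behavioral outcomes listed above", set apart in the same sentence from pre-post change for attitudes.
- Protocol section 5: for R1 and R2, change "from pre to 1-year follow-up estimates the maximum amount of benefit" attributable to the services.
- Protocol sections 9.3 and 9.5: T2 follows the final workshop session and reaches only completers who attend it. T3 comes about a year after enrollment and is sought from everyone enrolled. Planned response is 100% at T1, 90% at T2 and 70% at T3.

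Two other SAP rules use pre and post without distinguishing outcomes. Under *Defining analysis measures*, change in every composite is taken between the "pre-program composite score and post-program composite score". Under *Handling missing data*, for single items, "participants who do not respond to the item on either the pre- or post-survey will be excluded from the analytic sample for that outcome".

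**The concern.** The groups fit an outcome measured at exit. Among R1-R4 that is parenting attitudes (R4), which is secondary. For R1 and R2 the loss that matters is failure to answer at one year, and the stated groups do not separate fathers on it. The two losses also arise differently: missing the exit survey mainly reflects leaving the program or missing its last session, while missing the follow-up reflects failed tracking.

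Nothing else in the plan fills the gap. Protocol section 9.5 describes tracking, and answers the question on monitoring attrition with a list of incentives. The SAP does not impute missing outcomes, so the paired t-tests for R1 and R2 use only fathers with follow-up data. This comparison is the only planned look at whether those fathers differ from the rest. If it examines the wrong wave, similar groups would say little about selective loss at one year.

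**Working it through.** The documents give no counts for the four groups, so there is no stated figure to reproduce. The planned response rates in protocol section 9.5 bound the misclassification on the literal reading.

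**Inputs**, as shares of enrolled fathers: entrance 1.00; exit e = 0.90; follow-up f = 0.70. The overlap j (answered both exit and follow-up) is not given. It must lie between e + f - 1 = 0.60 and min(e, f) = 0.70. If the two responses were independent, j = 0.90 × 0.70 = 0.63.

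With entrance at 100%, the no-survey and post-only groups are empty among enrolled fathers. The check becomes a contrast between fathers with the exit survey (0.90, complete case) and those without it (0.10).

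| Quantity | Formula | j = 0.60 | j = 0.63 | j = 0.70 |
|---|---|---|---|---|
| Called complete case, no follow-up | e - j | 0.30 | 0.27 | 0.20 |
| As share of the complete-case group | (e - j)/0.90 | 33% | 30% | 22% |
| As share of follow-up non-respondents | (e - j)/0.30 | 100% | 90% | 67% |
| Has entrance and follow-up, not called complete | f - j | 0.10 | 0.07 | 0.00 |
| Neither exit nor follow-up | 1 - e - f + j | 0.00 | 0.03 | 0.10 |

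In the independent case, 0.27/0.90 = 30% of the complete-case group and 0.03/0.10 = 30% of the remainder lack follow-up. The two groups then do not differ at all in follow-up loss.

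The upper ends (30%, 33%, 100%) require every father who missed the exit survey to answer at one year. If fathers who missed exit are no more likely than others to answer later (an assumption), j lies between 0.63 and 0.70. The ranges narrow to 20-27% of enrolled fathers, 22-30% of the complete-case group and 67-90% of follow-up non-respondents.

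The Applicant Characteristics Survey is given before the enrollment decision (protocol section 9.2). The no-survey group may therefore hold applicants who never enrolled; they lie outside these figures.

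**The case against.** The strongest reply is that *post* is often generic here. Protocol section 1.1 describes primary and secondary outcomes together as assessed pre to post, although R1-R3 in that section are one-year questions. The SAP's change-score and single-item rules say pre and post for variables with a follow-up suffix. Since the analysis is promised per primary outcome, *post-survey* could mean the later survey for that outcome. Follow-up loss would then be examined, and the percentages above would not arise. That reading is possible, so the size is conditional on the literal one. It does not settle the text: *Identify study sample* separates exit from follow-up, *Analytic approach* separates pre-post from one-year change, and the protocol keeps T2 and T3 apart. An analyst coding the groups has no instruction to use follow-up.

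It is also fair to say that the groups feed a descriptive comparison and that no adjustment method is specified. The grouping alone changes no primary estimate. It limits what the comparison can show.

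Three stronger readings are tempting but unsupported:

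- *The plan certainly ignores follow-up loss, or leaves the wave for R1 and R2 open.* The loose wording prevents certainty on the first. On the second, protocol section 5 and the SAP's sample and analysis paragraphs assign the follow-up, even though section 9.3 also collects the behavioral measures at exit.
- *The primary test uses the wrong sample.* The SAP defines it correctly as entrance plus follow-up.
- *The percentages convert to counts by dividing the analytic sample of 483 by 70%.* Protocol section 8.2 gives the same 483 for parenting attitudes, an exit outcome with 90% planned response, so enrollment cannot be recovered this way.

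**Conclusion.** The concern holds as a defect of wording that should be fixed. As written, the check promised for R1 and R2 does not group fathers by the survey on which those outcomes depend. On the literal reading and the planned rates, 20-30% of enrolled fathers would be complete cases without a primary outcome, and 0-10% with usable primary data would not be complete cases. The ranges rest on the 100%, 90% and 70% planned response and on no assumption about overlap. If the authors meant the later survey for each outcome, only the clarification remains. The consequence is possible false reassurance about a 30% planned loss; the documents do not show that the primary estimates are biased.

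A separate, minor inconsistency concerns timing. Protocol sections 1.1 and 4 put R1-R3 one year after services are completed. Sections 1.2 and 9.3 put them one year after enrollment. The SAP follows the latter for the account items: "we will descriptively report the percent of participants who opened a checking or savings account one year after enrollment".

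**What to change.** 1. Under *Assessing non-response bias*, define the groups for R1 and R2 by entrance and one-year follow-up response: neither, entrance only, follow-up only, and both, with only the last called complete case.
2. Align the change-score rules and the single-item exclusion rule with the waves the SAP already assigns: entrance and follow-up for behavioral outcomes, entrance and exit for parenting attitudes. The descriptive one-year comparison of the account items can stay as it is.
3. As a separate minor correction, reconcile the wording of R1-R3 and their hypotheses with the planned follow-up timing of one year after enrollment.

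The cost is a few sentences in the SAP and one phrase in the research questions and hypotheses. Follow-up response status and the applicant characteristics are already collected, so no new data are needed.

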### 9.3. METHODS OF DATA COLLECTION

*If the evaluation will collect multiple waves of data, describe the timing of these waves below. When describing follow-up periods, specify whether the follow-up period will be post-baseline, post-random assignment, or post-program completion.*

Wave of Data Collection (e.g., baseline, short-term follow-up, long-term follow-up)	Timing of Data Collection
T1: baseline/pre-participation	Before first workshop session, at the same time as the nFORM entrance survey-following informed consent
T2: post-participation	After the final workshop session, at the same time as the nFORM exit survey
T3: 1-year follow-up	Collected approximately one year after program enrollment/baseline

*For each measure, describe how data will be collected detailing which data collection measures will be collected by which persons, and at what point in the programming or at what follow-up point.*

Measure	Timing of Data Collection (baseline, wave of data collection)	Method of Data Collection	Who Is Responsible for Data Collection?	Impact Evaluations Only: Will Methods or Collection Procedures Differ by Study Group?	Administrative Data Only: Will data access require data sharing agreement?

Parenting Behavior (interaction with children)
 
1 item: hours spent w/children in last 30 days (interval); 1 item: frequency reach out to children (categories, 5-point scale); 7 items: frequency engage in key behaviors (categories, 5-point scale)
	
nFORM Community Fathers Entrance Survey- administered at first workshop session/OLLE Pre;
 
nFORM Community Fathers Exit Survey- administered at last workshop session/OLLE Post/OLLE Follow-Up
	
nFORM and/or OLLE
 
Participant self-enters survey using online data collection platform
	
Case Manager/Facilitator will proctor data collection and assist participants as necessary
		

Co-Parenting Behavior
 
11 items: frequency of agreement with key co-parenting behaviors (interval, 5-point scale)
	
nFORM Community Fathers Entrance Survey- administered at first workshop session/OLLE Pre
 
nFORM Community Fathers Exit Survey- administered at last workshop session/OLLE Post/OLLE Follow-Up
	
nFORM and/or OLLE
 
Participant self-enters survey using online data collection platform
	
Case Manager/Facilitator will proctor data collection and assist participants as necessary
		
Father Financial Behavior	nFORM Community	nFORM and/or OLLE	Case Manager/Facilita		

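### The one-year analyses of parenting and co-parenting behavior (R1, R2) use only entrance and one-year pairs and leave out the exit scores, which most fathers lost at one year should have

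*SAP*

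**What the plan says.** - **Test.** SAP 1, Analytic approach: "We will use paired sample t-tests to assess the magnitude and significance of changes among program participants in the analytic sample for each outcome". For behavior the aim is to "assess pre-to-one-year follow-up change scores in the behavioral outcomes listed above among program participants before and after primary workshops".
- **Sample.** SAP 1, Identify study sample, admits consented participants who "took both an entrance and exit survey (for attitudinal outcomes) or entrance and follow-up survey (for behavioral outcomes").
- **Missing outcomes.** SAP 1, Handling missing data: "We will not be imputing truly missing values for outcomes".
- **Waves.** For both parenting and co-parenting behavior, the Protocol 9.3 table lists the entrance survey and then "nFORM Community Fathers Exit Survey- administered at last workshop session/OLLE Post/OLLE Follow-Up". Behavior is therefore measured at T1 (entrance), T2 (exit) and T3 (one year).
- **Response.** Protocol 9.5 expects "T2: 90%-Estimated completion rate" and, at T3, "70%-Estimated 1 year follow-up". It adds that exit surveys reach only completers present at the last session, and that one-year follow-up covers everyone enrolled on an intent-to-treat basis.
- **Non-response.** SAP 1, Assessing non-response bias, compares response groups on demographics and main reason for joining, taken from the applicant survey. It promises adjustment but names no method. Its groups are defined by pre- and post-survey and do not single out fathers with an exit survey but no one-year survey.

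**The concern.** R1 and R2 are confirmatory, and without a control group the mean change is the whole of the evidence. About 30% of fathers are expected to give no one-year score. The planned analysis drops them, including those whose behavior was measured at exit. If the fathers who can be found at one year differ in how much they changed, the mean among pairs is not the mean change among enrolled fathers. Exit scores carry information on this. Neither the test nor the non-response comparison uses them, and the intent-to-treat principle of the follow-up survey is not carried into the analysis.

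**Working it through.** **1. How many lost fathers should have an exit score (from Protocol 9.5).** Lost at T3: 100 − 70 = 30 per 100. No exit score: 100 − 90 = 10 per 100. Even if all 10 are among the 30 lost, 30 − 10 = 20 have an exit score, and 20/30 = 67%. If T2 and T3 response were independent the share would be 90%; the maximum is 100%. Only completers at the last session give exit scores, and they probably overlap with those found at one year, so the realistic share is nearer 67%. With exit response r2, the lower bound is (0.30 − (1 − r2))/0.30, which exceeds one half only while r2 is above 0.85.

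Enrollment is not given in the text available. If the 483 in Protocol 8.2 is the analytic sample at 70%, enrollment is 483/0.70 = 690. Then 207 are lost, of whom 138 to 207 have exit scores.

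**2. The plan's own precision figure.** Protocol 8.2 states a minimum detectable effect of 0.030 with 483 fathers, two-sided 0.05 and 80% power. A paired test gives (1.960 + 0.842)/√483 = 0.1275 SD of change, so 0.030 does not reproduce. That is a separate matter, and nothing below uses it.

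**3. What the paired test needs.** Assume unit SDs, normal scores and correlations r12 = 0.5, r23 = 0.6, r13 = 0.5 (none are in the documents). If one-year response depends on a standardized variable X, the bias of the paired mean is Cov(T3 − T1, X) times the shift in the mean of X among responders. The covariances are:

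- X = entrance-to-exit improvement: (r23 − r13 − r12 + 1)/√(2(1 − r12)) = 0.6/1 = 0.6
- X = exit level: r23 − r12 = 0.1
- X = entrance level: r13 − 1 = −0.5
- X = one-year level: 1 − r13 = 0.5
- X = entrance-to-one-year improvement: √(2(1 − r13)) = 1

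So the condition is that response be unrelated to the T1-to-T3 change. Dependence on exit level alone does almost nothing here, and nothing at all if r23 = r12.

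**4. Simulation.** 690 enrolled, 90% with T2, 70% with T3, true change zero, 400 replicates. Log-odds slopes are 0.3/0.5/0.7 per SD (odds ratios 1.35/1.65/2.0).

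| One-year response depends on | Paired bias (SD) | Three-wave likelihood model (SD) |
|---|---|---|
| Entrance-to-exit improvement | about +0.05 to +0.12 | about 0.00–0.01 |
| Exit level | about +0.01 to +0.02 | about 0.00–0.01 |
| Entrance level | about −0.05 to −0.10 | about 0.00–0.01 |
| One-year level | about 0.05 to 0.10 | about 0.05 to 0.13 |
| Entrance-to-one-year improvement | 0.089/0.142/0.193 | 0.054/0.087/0.120 |

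In the first row the paired test is significant in about 21% to 75% of replicates across repeated runs; in the second, 4% to 7%. In the least favorable overlap for the first row (every missing exit score among T3 non-responders), the model's bias stays at or below 0.018 SD.

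**5. Precision with no selective loss.** Paired variance is 2(1 − r13)/(0.7N). Against the three-wave model, relative efficiency is 1.125 to 1.136 at the correlations above, a variance cut of 1 − 1/1.125 = 11% to 1 − 1/1.136 = 12%. Over the other correlation sets tried it is 1.08 to 1.23 (a cut of 7% to 19%). With 690 enrolled, the detectable change falls from 0.128 to about 0.120 SD.

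**The case against.** **Stronger readings that a reader might infer.**

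- *The paired test overstates improvement and can make an ineffective program look effective.* The documents give no response mechanism or wave correlations, and the table shows that the sign can go either way. Protocol 5 also concedes that there is no counterfactual, so neither analysis isolates a program effect.
- *Dropping these fathers is valid only if one-year response is unrelated to how they were doing at exit.* That is the wrong condition. With all correlations at 0.5 and response driven by exit level, the bias is 0.001 SD and the rejection rate 4%.
- *The exit scores would correct the bias.* They do so only if, given entrance and exit scores, loss is unrelated to the one-year score. If reachability follows the one-year score, the model can be slightly worse.

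**Other points against.** The 90% and 70% are planning estimates. Fathers who left the program have no exit score and may be the hardest to find at one year; those missing both add only an entrance score. The SAP calls the study descriptive and does promise a non-response analysis, though on applicant-survey variables only. Protocol 1.1, 1.2 and 4 frame R1 and R2 around fathers who complete services, so analyzing all enrolled fathers changes whom the estimate describes. The simulations used normal data, whereas fathers who have not seen their child are set to the scale floor.

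All of this stands and limits the claim. It does not give the exit scores a use that the plan lacks. The composite definition in SAP 1, Defining analysis measures, speaks of a post-program score, which might be read as the exit score. The sample rule and the analytic approach both name the follow-up survey for behavior.

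**Conclusion.** The point holds as a choice of method. Behavior at exit is collected for both primary constructs, no specified R1 or R2 analysis uses it, and on the plan's own rates at least two-thirds of the fathers lost at one year should have it. A three-wave likelihood model keeps the T3-minus-T1 contrast and, with complete data, gives the same mean change. Under the assumed correlations it removes nearly all the bias when loss follows entrance or exit scores, and it gains a moderate amount of precision when loss is not selective.

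That the R1 and R2 results will be biased, or biased upward, is not shown. The magnitudes rest on assumed enrollment, correlations, normality and response slopes. The model does not cure loss that depends on the unseen one-year score, nor the lack of a control group. The change should be made, but the planned test is not invalid in itself.

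**What to change.** 1. For the parenting-engagement and co-parenting composites (ENGAGFU, COPARFU), estimate T3 minus T1 from a likelihood-based repeated-measures model with T1, T2 and T3 as categorical time and an unstructured covariance. Include every consented father with an entrance survey.
2. State the target population. Reconcile the intent-to-treat wording of Protocol 9.5 with the completer wording of Protocol 1.1, 1.2 and 4.
3. Report the planned paired t-test alongside as a sensitivity analysis.
4. In the non-response comparison, add exit behavior and entrance-to-exit change, separate exit-only from one-year responders, and name the adjustment method.
5. HOURSFU is likely to be skewed and REACHFU is a single ordinal item. For these, use robust or bootstrap standard errors or keep the paired analysis.
6. Make the composite change definition in the SAP name the one-year survey for behavior.

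Cost: a few SAP lines and one model per composite, with no new data collection; SPSS, the evaluator's preferred package (Protocol 10), can fit it. The price is a missing-at-random assumption given T1 and T2, which must be stated, and a result slightly harder to explain than a paired t-test.
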